9.4.6.1 Selection of Timing of Dose for Each Subject

9.4.7 Blinding

An independent third-party vendor will develop the randomization schedule so that site personnel will not know treatment assignments. BMN 111 or placebo will be labeled with the study number and a unique identification number. Subjects and the participating site members will be blinded to the two study treatments (15 µg/kg BMN 111 or placebo). The investigator and other members of staff involved with the study will remain blinded to the treatment randomization code during the assembly procedure. In the event of an emergency medical situation where subject management would be determined or significantly altered by knowing the treatment assignment, the investigator may be unblinded without prior written approval from the Medical Monitor. Following such an emergency unblinding, the investigator will contact the medical monitor and provide written rationale according to the unscheduled unblinding procedure set forth in the Study Manual. The Medical Monitor will review the rationale, evaluate whether there are any additional safety considerations that need to be implemented for the subject and/or the study, and determine whether the investigator requires further guidance on unblinding. The Medical Monitor may also communicate with the investigator advice on the care of the subject and define the plan for the subject's future participation in the study.

9.4.8 Prior and Concomitant Medications

All medications (prescription, over-the-counter [OTC] and herbal), and nutritional supplements 30 days prior to screening and throughout the study will be recorded on the designated eCRF. The Investigator may prescribe additional medications during the study, as long as the prescribed medication is not prohibited by the protocol. In the event of an emergency, any needed medications may be prescribed without prior approval, but the medical monitor must be notified of the use of any contraindicated medications immediately thereafter. Any concomitant medications added or discontinued during the study should be recorded on the eCRF.

9.5 Treatment Compliance

Subjects will be instructed to return all used and unused BMN 111 or placebo kits at each study visit. Subject compliance with the dosing regimen will be assessed by reconciliation of

the used and unused vials. The quantity dispensed, returned, used, lost, etc. must be recorded on the dispensing log provided for the study.

The date, time, and volume of each dose of BMN 111 or placebo administered to each subject must be recorded. These data will be used to assess treatment compliance.

9.6 Investigational Product Accountability (BMN 111 or Placebo)

The Investigator or designee is responsible for maintaining accurate records (including dates and quantities) of IP(s) received, subjects to whom IP is dispensed (subject-by-subject dose specific accounting), and IP lost or accidentally or deliberately destroyed. The Investigator or designee must retain all unused or expired study supplies until the study monitor (on-site CRA) has confirmed the accountability data.

9.6.1 Return and Disposition of Clinical Supplies

Unused BMN 111 or placebo must be kept in a secure location for accountability and reconciliation by the study monitor. The Investigator or designee must provide an explanation for any destroyed or missing BMN 111 or placebo kits/vials.

Unused BMN 111 or placebo may be destroyed on site, per the site's standard operating procedures, but only after BioMarin has granted approval for destruction. The study monitor must account for all BMN 111 or placebo kits/vials in a formal reconciliation process prior to destruction. The site must document all BMN 111 or placebo destroyed on site, and documentation must be provided to BioMarin and retained in the investigator study files. If a site is unable to destroy BMN 111 or placebo appropriately, the site can, upon request, return unused BMN 111 or placebo to the BioMarin contracted facility. The return of all BMN 111 or placebo kits/vials must also be documented and accounted for per instructions provided by BioMarin.

All BMN 111 or placebo and related materials should be stored, inventoried, reconciled, and destroyed or returned according to applicable state and federal regulations and study procedures.

9.7 Dietary or Other Protocol Restrictions

BMN 111 will be administered as a single daily dose of 15 µg/kg SC injection given daily at approximately the same time each day whenever possible. Placebo will be administered as a single SC injection given daily at approximately the same time each day whenever possible. Following administration of each dose, subjects will be observed for at least 2 hours after the injection for observation for Days 1 to 3, and 30 minutes for all other days of dose administration.

Subjects should have adequate food intake prior to dosing. All subjects should have been well hydrated and fed in the hour prior to administration of BMN 111 or placebo.

9.8 Demographic Data and Medical History

Demographic data and a detailed medical history will be obtained at Screening. This medical history, including growth history and ACH-related history, should elicit all major illnesses, diagnoses, and surgeries that the subject has ever had; any prior or existing medical conditions that might interfere with study participation or safety; and evaluation for knee, thigh, hip or groin pain, or change in gait/activity.

9.9 Biological Parental Standing Height

Standing height of the subject's biological parents (optional) may be assessed via height measurement or stated height. Height measurement can be done at any point in the study. Prior to the measurement being taken, each parent is required to complete an ICF specific to parent height assessment. The ICF will be signed prior to the assessment, which can be done at any point in the study. If the biological parent is not available during the course of the study to take his/her standing height, if consented, the biological parent can provide his/her stated height.

9.10 Physical Examination Findings

Physical examination will include assessment of general appearance; CV; dermatologic; head, eyes, ears, nose, and throat; lymphatic; respiratory; GI; musculoskeletal; and neurological/psychological and genitourinary. Other body systems may be examined. Screening results will be the baseline values and clinically significant changes from baseline will be recorded as an AE or SAE and study drug related or unrelated when appropriate based on the investigator's clinical judgment.

9.11 Echocardiogram

Cardiac anatomy and function will be evaluated by a standard 2-dimensional Doppler echocardiogram by a cardiologist. Echocardiograms will be performed at screening, and provide information regarding cardiac anatomy and function prior to enrollment in the study.

9.12 Efficacy and Safety Variables

9.12.1 Efficacy and Safety Measurements Assessed

The Schedule of Events (Table 9.1.1 and Table 9.1.2) describes the timing of required evaluations.

9.12.2 Primary Efficacy Variables

The primary efficacy endpoint is change from baseline in length/height Z-score.

Growth measures may be collected approximately the same time each visit (\pm 2 hr from the time when the first measurement assessment was taken at Screening) by a study staff member, preferably the same person throughout the study, who has been trained by a BioMarin representative. Standardized measuring equipment and detailed measurement techniques are detailed in the Anthropometric Measurement Guidelines.

9.12.3 Secondary Efficacy Variables

The secondary efficacy endpoints include change from baseline in AGV (annualized to cm/yr), biomarker samples to evaluate the effect of BMN 111 on bone metabolism, BMN 111 pharmacodynamic biomarkers, growth parameters and body proportions, sleep apnea, skull and brain morphology, and clinical outcome assessments (developmental/functional/HRQoL status).

Weight will be measured at Screening and at study visits as indicated on the Schedule of Events ([Table 9.1.1](#) and [Table 9.1.2](#)).

Biomarkers may include but are not limited to assessment of changes in bone and collagen metabolism (serum bone-specific alkaline phosphatase, serum collagen type X, and urine C-terminal telopeptide of collagen type II [CTX-II]) and BMN 111 bioactivity (plasma and urine cGMP). BioMarin or designee will perform analysis, and samples may also be used for assay development.

Samples for blood and/or urine biomarkers will be collected at the time points presented in the Schedule of Events ([Table 9.1.1](#) and [Table 9.1.2](#)). Refer to the Study Laboratory Manual for instructions regarding obtaining and shipping samples. The sample type will also be included in the Study Laboratory Manual.

9.12.3.1 Body Proportion Ratios of the Extremities

Change from baseline in body proportion ratios of the extremities will be evaluated using anthropometric measurements and measurement ratios. Refer to the Anthropometric Measurement Guidelines for specific instructions regarding the collection of growth measurements. All age-appropriate physical measurements will be collected at approximately the same time each visit (\pm 2 hours around the time when the first measurement assessment was taken at Screening) by a trained study staff member; every effort will be made to have the measurements collected by the same study staff member, if possible, throughout the study. Each measurement will be taken in triplicate (excluding weight, taken once).

Anthropometric measurement can be conducted either pre-dose or post-dose. Measurements may include but are not limited to length, standing height (if able to stand unsupported), crown-to-rump length, head circumference, upper and lower arm and leg, and arm span. Measurements not taken in the midsagittal plane should be taken on the right side of the body if possible and should always be taken on the same side of the body throughout the study. Body proportion measurements may include but are not limited to upper arm:forearm length ratio, upper leg:lower leg length ratio, and armspan:standing height ratio.

9.12.3.2 MRI Assessments

[figure not shown]
MRIs are performed to evaluate the effect of BMN 111 on skull and brain morphology, including foramen magnum, ventricular, and brain parenchymal dimensions. MRI assessment procedures for all visits must be performed as described in the Imaging Manual and can be conducted either pre-dose or post-dose.

9.12.3.3 Sleep Study

Given that sleep apnea is a finding in children with ACH (Waters, 1993) and has implications on functional and health outcomes, a sleep study will be performed in a limited number of qualified sleep centers. A sleep-testing device will be used to assess the presence and severity of sleep-disordered breathing by measurement of blood oxygen saturation, pulse rate, and airflow during overnight monitoring. Assessment of episodes of sleep apnea will include, but may not be limited to, the number of episodes of apnea and hypopnea per hour (Apnea/Hypopnea Index).

9.12.3.4 Clinical Outcome Assessments

Clinical outcome assessments will be administered to assess the HRQoL of study subjects. Functional Independence will be assessed. Clinical outcome assessments will be performed at the time points indicated in the Schedules of Events (Table 9.1.1 and Table 9.1.2) and the ITQoL should be administered prior to any other assessments. The Wee-FIM and the Bayley-III may be administered at any point deemed convenient during the visit. The age ranges for clinical outcome assessment tools are shown in Figure 9.12.3.4.1. The clinical outcome assessments are not to be considered as source data for AEs.

Figure 9.12.3.4.1: Clinical Outcomes Assessment Tools

9.12.3.4.1 Bayley-III

The Bayley-III is a performance-based outcome assessment for use in children from 1 to 42 months. It is individually administered by the trained clinician to the subject/child. The time required varies from 15-60 minutes depending on the child's developmental level and cooperation.

Scales include Cognitive subscale, Receptive and Expressive subscales, and Gross and Fine Motor subscales. The two language scales make up a composite Language Scale score and the Gross and Fine Motor subscales yield a composite Motor Scale score.

The scales have clinical and research utility as a diagnostic assessment for young children with varied disorders and disabilities, and reflect current professional standards for early childhood assessment (Bayley, 2006).

In addition to its use for subjects ranging from 1 to 42 months old, the Bayley-III assessment will be administered to those entering the study between 42 and 60 months old (Figure 9.12.3.4.1) and for the remainder of the duration of this study, as this assessment can capture ongoing developmental issues associated with Achondroplasia. Bayley-III is waived for subjects <1 month old.

9.12.3.4.2 Functional Independence Measure (Wee-FIM)

The Wee-FIM instrument is an assessment tool that measures functional performance across three domains (self-care, mobility and cognition) (Ireland, 2011; Ireland, 2012).

The Wee-FIM instrument has been used in previous research in children with ACH, and has identified ongoing limitations in functional performance across these domains extending

beyond the age of 7 years ([Ireland, 2011](#)). Because the Wee-FIM considers the child's performance from a caregiver's perspective ([Ireland, 2012](#)), this tool in turn gives an indication of "burden of care" for families and caregivers of children with ACH. Wee-FIM is waived for children < 6 months old.

9.12.3.4.3 Infant and Toddler Quality of Life Questionnaire (ITQOL)

The Infant Toddler Quality of Life questionnaire (ITQOL) is an observer-reported outcome tool developed for use in children from 2 months to 5 years old that attempts to capture physical, mental and social well-being. The ITQOL adopts the World Health Organization's definition of health as a state of complete physical, mental and social well-being, and not merely the absence of disease. The ITQOL also assesses the quality of the parent/guardians life. The 97-item full-length version (ITQOL) will be used for this study. Completion time varies. ITQOL is waived for subjects < 2 months old. The ITQOL should be administered prior to any other study assessments.

9.12.4 Exploratory Efficacy Variables

9.12.4.1 Clinical Photography

To document the physical and phenotypic findings of achondroplasia with and without treatment with study drug, clinical photography of the full body, face, spine, and extremities will be conducted. This assessment is optional. If the parents/caregivers decline clinical photography, the assessment will be waived for the duration of the study.

9.12.4.2 Exploratory Biomarker Research Sample Analyses

All samples collected in this study may be used for on-study exploratory biomarker research once the primary use has been completed.

For each portion of the blood and urine samples reserved for protocol-specified analyses, there may be multiple sample aliquots. Once samples have been successfully analyzed during the study, unused sample portions may be used during the study for assay development or other purposes stated in this section. No exploratory genomic research will be conducted without consent from the subject and his/her legally authorized representative (parent or legal guardian).

9.12.4.3 Genomic Biomarker Analysis

While the inherited FGFR3 mutations associated with achondroplasia are well characterized, disease phenotype in monogenic diseases is often modified by variants in other genes. Exploratory genomics will include, but are not limited to NPR-B, BRAF, and other genes associated with CNP signaling. Exploratory genomic analysis may inform understanding of

the BMN 111 mechanism of action in achondroplasia. This analysis will not be conducted without express consent from the subject and his/her legally authorized representative (parent or legal guardian).

9.12.5 Pharmacokinetics Variables

PK plasma samples will be collected pre-dose and at 5 (\pm 2 min), 15 (\pm 2 min), 30 (\pm 5 min), 45 (\pm 5 min), 60 (\pm 5 min), 90 (\pm 5 min), and 120 (\pm 5 min) minutes post-dose. On Day 1, additional PK samples will be collected at 180 (\pm 5 min) and 240 (\pm 5 min) minutes. In the event of interruption of study drug administration for a sentinel patient on Day 1 when PK samples are scheduled, the collection of PK samples should be delayed until the subsequent day and only performed after successful administration of study drug has been completed in a single injection.

Whenever possible, the following PK parameters for sentinel subjects and for subjects randomized to BMN 111 will be estimated by non-compartmental analysis:

- Area under the plasma concentration-time curve from time 0 to infinity ($AUC_{0-\infty}$)
- Area under the plasma concentration-time curve from time 0 to the time of last measurable concentration (AUC_{0-t})
- Maximum observed plasma concentration (C_{max})
- Time to reach C_{max} (T_{max})
- Elimination half-life ($t_{1/2}$)
- Apparent clearance (CL/F)
- Apparent volume of distribution (V_z/F)

Refer to the Study Laboratory Manual for additional instructions regarding obtaining and shipping samples. BioMarin will perform sample analysis, and samples may also be used for assay development.

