8 STUDY OBJECTIVES

The primary objectives of the study are to:

- Evaluate the safety and tolerability of BMN 111 in children age 0 to < 60 months with ACH
- Evaluate the effect of BMN 111 on change from baseline in length/height Z-score

The secondary objectives of the study are to:

- Evaluate the effect of BMN 111 on change from baseline in AGV throughout the 52 weeks of the study
- Evaluate the effect of BMN 111 on bone morphology/quality by X-ray and dual X-ray absorptiometry (DXA)
- Evaluate the PK of BMN 111 in children age 0 to < 60 months with ACH
- Evaluate hip function
- Evaluate for hip, thigh, or knee pain, or change in gait
- Evaluate the effect of BMN 111 on HRQoL, developmental status, and /functional independence using age-specific QoL and functional independence questionnaires/QOL status (Bayley Scales of Infant and Toddler Development, Third edition [Bayley-III], Activity of Daily Living and Functional Independence Measure (Wee-FIM), Infant Toddler Quality of Life Questionnaire (ITQOL), Child Behavior Checklist (CBCL))
- Evaluate immunogenicity of BMN 111 and assess impact on safety, PK, and efficacy measures
- Evaluate the effect of BMN 111 on bone metabolism and BMN 111 pharmacodynamic biomarkers
- Evaluate the effect of BMN 111 on growth parameters and body proportions, including change from baseline in upper:lower body segment ratio
- Evaluate the effect of BMN 111 on sleep apnea
- Evaluate the effect of BMN 111 on skull and brain morphology, including foramen magnum, ventricular and brain parenchymal dimensions
- Describe the incidence of surgical interventions, including cervical decompression, adenotonsillectomy, and tympanostomy

The exploratory objectives of the study are to:

- Document physical and phenotypic changes with clinical photography (optional)
- Evaluate genomic biomarkers (optional)

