Vitamin D, 25-hydroxy test	X												X	
Salivary cortisol	X										X		X	X
Serum prolactin	X										X		X	X
Plasma PK and cGMP assessments ^l		X						X		X	X	X		
Anti-BMN 111 immunogenicity ^m		X				X		X		X		X		X

Procedure ^a	Screening/ Baseline Day -30 to Day -1 ^b	Day 1	Day 2	Day 3	Day 8 (±1d)	Week 3 (±7d)	Week 6 (±7d)	Week 13 (±7d)	Week 20 (±7d)	Week 26 (±7d)	Week 39 (±7d)	Week 52 (±7d)	Week 56 Safety Follow-Up (+7d) ^{aa}	Early Term Visit
Genomic biomarkers (optional) ⁿ	X													
Bone metabolism blood biomarkers ⁿ	X				X		X		X		X			X
Bone metabolism urine biomarkers ^o		X	X	X		X		X		X	X	X		X
BMN 111 PD urine biomarkers ^o		X	X	X		X		X		X	X	X		X
Urine chemistry ^o		X	X	X		X		X		X	X	X		X
Hip monitoring ^p										X		X		X
MRI brain/skull ^q	X											X		X
Sleep study ^r	X											X		X
Clinical outcome assessment: Bayley-III	X									X		X		X
Clinical outcome assessment: Wee-FIM ^s	X									X		X		X
Clinical outcome assessment: ITQOL ^s	X									X		X		X
Safety assessment: CBCL ^s	X									X		X		X
DXA (BMD and BMC) of whole body [less head], spine) ^t	X											X		X ^t
AP and lateral X-rays of spine ^u	X											X		X ^u
AP X-rays of lower extremities ^u	X											X		X ^u
Clinical photographs (optional) ^v	X											X		X

Procedure ^a	Screening/ Baseline Day -30 to Day -1 ^b	Day 1	Day 2	Day 3	Day 8 (±1d)	Week 3 (±7d)	Week 6 (±7d)	Week 13 (±7d)	Week 20 (±7d)	Week 26 (±7d)	Week 39 (±7d)	Week 52 (±7d)	Week 56 Safety Follow-Up (+7d) ^{aa}	Early Term Visit
Capture concomitant procedures/interventions/surgeries													X	X
BMN 111 or placebo administration ^w														
BMN 111 or placebo accountability														X
Adverse events ^x													X	X
Concomitant medications ^y	X												X	X
Phone call ^z														
Home health visit														

^a Clinic visits (except Days 1, 2, 3, and 8) have a ± 7-day window. Anthropometric measurement and imaging assessments can be conducted either pre-dose or post-dose.

^b If the 111-901 visit at which the subject enters Study 111-206 and the 111-206 Screening visit are on the same day, the procedures common to both visits will be performed one time only. All blood tests at Screening visit should be obtained between Day -30 and Day -14.

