The criteria for dose adjustment are based on obtaining equivalent exposure characterized to be safe and effective with the 15 μ g/kg dose in Study 111-202 in each of the age cohorts evaluated in this study. BMN 111 dose may be adjusted if the mean observed AUC_{0-120} from

sentinel subjects is less than the 25th percentile for AUC₀₋₁₂₀ in Cohort 3 (15 µg/kg) of Study 111-202 or greater than the 75th percentile in Cohort 3 of Study 111-202. If these criteria are met, an allometric scaling coefficient, α , for BMN 111 clearance by subject body weight will be determined using a population PK modelling approach and available data from this study and Studies 111-202 and 111-101. The recommended adjusted dose will be determined using the following expression:

$$Dose_{ch} = Dose_{ref} \left(\frac{WT_{ch}}{WT_{ref}} \right)^\alpha$$

where WT_{ref} and $Dose_{ref}$ are the typical (i.e., median) subject body weight and total dose, respectively, at the 15 µg/kg dose level in Cohort 3 of Study 111-202, and WT_{ch} is the anticipated median weight in the age cohort being studied. As such, the recommended adjusted dose will target the median AUC₀₋₁₂₀ observed at the 15 µg/kg dose level of Study 111-202. The recommended adjusted dose, $Dose_{ch}$, will be normalized by WT_{ch} , to provide the recommended adjusted weight-based dose. The following rules will be used for dose adjustment:

- A maximum of a 2-fold increase in dose/kg will be permitted between dose adjustments regardless of exposure.
- The total dose will not exceed the highest total dose administered in Study 111-202.

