14.4 Pharmacokinetic Analyses

Subjects randomized to receive BMN 111 or placebo will undergo pharmacokinetic testing.

For subjects randomized to BMN 111, PK parameters generated over the course of the study will be evaluated and summarized with descriptive statistical measures (mean, standard deviation, CV%, min, median and max). Correlative analyses of some of the PK parameters with efficacy, safety and immunogenicity measures may be conducted.

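### AUC0-t is the only observed exposure area on the PK list, but sampling runs to 240 min on Day 1 and 120 min later, so it is not like-for-like across visits

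*Protocol*

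**What the plan says.** **Sampling.** Section 9.12.5 and the PK footnote to Table 9.1.1 set samples pre-dose and at 5, 15, 30, 45, 60, 90 "and 120 (\pm 5 min) minutes post-dose". Then: "On Day 1, additional PK samples will be collected at 180" and 240 min. In Table 9.1.1 the row "Plasma PK and cGMP assessments" is marked at Day 1 and Weeks 13, 26, 39 and 52.

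**Parameters.** One list covers these visits: "Whenever possible, the following PK parameters for sentinel subjects and for subjects randomized to BMN 111 will be estimated by non-compartmental analysis". It contains AUC0-inf, AUC0-t, Cmax, Tmax, half-life, CL/F and Vz/F. AUC0-t is defined as "Area under the plasma concentration-time curve from time 0 to the time of last measurable concentration". The synopsis gives the same two areas. AUC0-120 appears in neither place.

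**Use.** Section 14.4 says that "PK parameters generated over the course of the study will be evaluated and summarized with descriptive statistical measures", and allows correlations with efficacy, safety and immunogenicity. Section 14.5 allows the same from the immunogenicity side. A secondary objective in section 8 is to "Evaluate immunogenicity of BMN 111 and assess impact on safety, PK, and efficacy measures".

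**The fixed-window area.** AUC0-120 does appear in section 9.1.1, as the trigger for dose adjustment ("BMN 111 dose may be adjusted if the mean observed" value in sentinel subjects lies outside an interquartile range from Study 111-202) and as the exposure that an adjusted dose targets.

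**The concern.** An area that stops at the last measurable sample is comparable between visits only if the last possible sample time is the same. Here it is 240 min on one visit and 120 min on the other four. AUC0-inf is also listed, but part of it is extrapolated, so AUC0-t is the only area made wholly of observed data.

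The programme has read repeat-dose exposure this way before. Section 7.2.1 reports AUC in adults as 33% above Day 1 after 10 days and concludes that change with repeat dosing is minimal. Antibodies induced by treatment can appear only after Day 1, so the shorter window coincides with the visits at which they could be present. A table of AUC0-t by visit could then suggest a loss of exposure that comes from the sampling schedule, or could hide a true rise.

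**Working it through.** The protocol states no figure for this, so there is none to reproduce. The check asks how far AUC0-t would differ between visits if the concentration profile were identical.

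**Inputs**
- Last sample: 240 min on Day 1, 120 min at Weeks 13-52 (section 9.12.5).
- Half-life 40-55 min and mean Tmax 15-26 min (section 7.2.1, healthy adults). Assumed to hold in infants and young children.
- Quantification limit: not given. Varied from 1% to 30% of Cmax.

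**Model.** One compartment, first-order absorption, no noise.
- ke = ln 2 / half-life: 0.0173 per min at 40 min, 0.0126 per min at 55 min.
- ka solved from Tmax = ln(ka/ke) / (ka - ke).
- Share of AUC0-inf reached by time T: F(T) = 1 - [ka exp(-ke T) - ke exp(-ka T)] / (ka - ke).

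| Half-life, Tmax (min) | ka (per min) | F(120) | F(180) | F(240) | F(120)/F(240) | F(120)/F(180) |
|---|---|---|---|---|---|---|
| 40, 15 | 0.169 | 0.861 | 0.951 | 0.983 | 0.876 | 0.905 |
| 40, 26 | 0.072 | 0.836 | 0.942 | 0.979 | 0.853 | 0.887 |
| 55, 15 | 0.195 | 0.764 | 0.889 | 0.948 | 0.806 | 0.860 |
| 55, 26 | 0.087 | 0.742 | 0.879 | 0.943 | 0.787 | 0.844 |

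**AUC0-t, later visit against Day 1**
- Measurable to 240 min on Day 1: 1 - 0.876 = 12% to 1 - 0.787 = 21% lower.
- Measurable only to 180 min: 1 - 0.905 = 10% to 1 - 0.844 = 16% lower.
- Nothing measurable after 120 min: no difference.

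**Which case applies.** Modelled concentrations are 18-36% of Cmax at 120 min, 6-17% at 180 min and 2-8% at 240 min. With a limit at 5% of Cmax, the last measurable Day 1 sample is at 180 min for a 40-min half-life and at 240 min for a 55-min half-life. At 10% of Cmax it is at 120 and 180 min respectively. At 20% of Cmax there is no effect anywhere in the adult range. If children clear the drug faster, with an assumed half-life of 15-30 min, the largest apparent fall is about 1-10%.

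**The other parameters.** A non-compartmental analysis of the same profiles (linear-up/log-down, terminal slope from the last three measurable points) on both sampling grids gave:
- AUC0-inf, later/Day 1 ratio: 1.000-1.006. CL/F follows it.
- Half-life: 40.0-41.5 min on the 120-min grid when the true value is 40, and 55.0-55.9 min when it is 55.
- Vz/F scales with CL/F times half-life, so its largest shift, against the 240-min grid (40.0 min), is about (41.5/40.0)/1.006 = 1.03.
- Extrapolated share of AUC0-inf, 1 - F: 14-26% with samples to 120 min, 2-6% with samples to 240 min. This is a loss of precision, not a fall.
- Cmax and Tmax: unchanged, because both grids are the same up to 120 min.

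AUC0-120 gives a ratio of exactly 1 for identical profiles, because its window is sampled at every PK visit.

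**The case against.** The strongest reply is that little depends on this. The only PK-driven rule, dose adjustment in section 9.1.1, already uses AUC0-120. Section 14.4 plans a descriptive summary and optional correlations, and no test of Day 1 against later visits is stated. An antibody effect can be examined between antibody-positive and antibody-negative children at the same visit, where the windows match. Cmax, AUC0-inf and CL/F in the same table would not show the fall, so a misreading of AUC0-t would be contradicted alongside it. The effect also needs measurable drug after 120 min. Section 9.1.1 says the same weight-based dose gave lower exposure in children than in adults and may give less than the target range here, which makes late samples more likely to fall below the limit. Shorter sampling after Day 1 also fits the stated aim of limiting blood volume.

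Most of this stands, and it limits the point. A reader might infer that exposure in general will appear to fall at every later visit, and only because of the window. The documents do not support that: one parameter is affected, the quantification limit is not stated, and doses may change through adjustment or ageing, so real changes can be mixed in. A reader might also infer that the terminal-phase parameters are biased downward; the calculation shows lower precision without a systematic shift.

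The reply does not make AUC0-t comparable. The qualifier about parameters being estimated whenever possible excuses those that cannot be derived, but AUC0-t can be computed from any measurable profile. Nor is this a detail left to the SAP, because the protocol itself fixes both the sampling times and the list.

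**Conclusion.** The point holds for AUC0-t alone. The sampling schedule and the parameter list together give an observed area that is not like-for-like between Day 1 and Weeks 13-52. The possible size is 12-21% if drug is measurable to 240 min on Day 1, 10-16% if only to 180 min, and zero if nothing is measurable after 120 min. These figures rest on adult half-life and Tmax carried over to young children and on a noise-free one-compartment model; a shorter half-life would make them smaller. What is exposed is the reading of PK over time and of its relation to antibodies, under a secondary objective. The primary endpoint is not touched. This is a cheap improvement, not a fault in any stated decision.

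**What to change.** Add AUC0-120 to the parameter list in section 9.12.5 and the synopsis, and name it in section 14.4. State there that AUC0-120, with Cmax, is the exposure measure for between-visit, antibody-PK and exposure-response analyses, and that AUC0-t is not compared between Day 1 and later visits. AUC0-t can stay on the list as a within-visit description. Acceptance limits for the terminal slope and the extrapolated share can be left to the SAP.

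The cost is one more derived parameter to report. No samples, visits or blood volume are added, because every PK visit already covers 0-120 min.
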